14.0 QUALITY CONTROL AND QUALITY ASSURANCE

14.1 Study-Site Monitoring Visits

Monitoring visits to the study site will be made periodically during the study to ensure that all aspects of the protocol are followed. Source documents will be reviewed for verification of data recorded on the CRFs. Source documents are defined as original documents, data, and records. The investigator and institution guarantee access to source documents by the sponsor or its designee (CRO) and by the IRB or IEC.

All aspects of the study and its documentation will be subject to review by the sponsor or designee (as long as blinding is not jeopardized), including but not limited to the Investigator's Binder, study medication, subject medical records, informed consent documentation, documentation of subject authorization to use personal health information (if separate from the informed consent forms), and review of CRFs and associated source documents. It is important that the investigator and other study personnel are available during the monitoring visits and that sufficient time is devoted to the process.

14.2 Protocol Deviations

The investigator should not deviate from the protocol, except where necessary to eliminate an immediate hazard to study subjects. Should other unexpected circumstances arise that will require deviation from protocol-specified procedures, the investigator should consult with the sponsor or designee (and IRB or IEC, as required) to determine the appropriate course of action. There will be no exemptions (a prospectively approved deviation) from the inclusion or exclusion criteria.

The site should document all protocol deviations in the subject's source documents. In the event of a significant deviation, the site should notify the sponsor or its designee (and IRB or EC, as required). Significant deviations include, but are not limited to, those that involve fraud or misconduct, increase the health risk to the subject, or confound interpretation of primary study assessment. A Protocol Deviation Form should be completed by the site and signed by the sponsor or designee for any significant deviation from the protocol.

14.3 Quality Assurance Audits and Regulatory Agency Inspections

The study site also may be subject to quality assurance audits by the sponsor or designees. In this circumstance, the sponsor-designated auditor will contact the site in advance to arrange an auditing visit. The auditor may ask to visit the facilities where laboratory samples are collected, where the medication is stored and prepared, and any other facility used during the study. In addition, there is the possibility that this study may be inspected by regulatory agencies, including those of foreign governments (eg, the FDA, the United Kingdom Medicines and Healthcare products Regulatory Agency, the Pharmaceuticals and Medical Devices Agency of Japan). If the study site is contacted for an inspection by a regulatory body, the sponsor should be notified immediately. The investigator and institution guarantee access for quality assurance auditors to all study documents as described in Section 14.1.

15.0 ETHICAL ASPECTS OF THE STUDY

This study will be conducted with the highest respect for the individual participants (i.e, subjects) according to the protocol, the ethical principles that have their origin in the Declaration of Helsinki, and the ICH Harmonised Tripartite Guideline for GCP. Each investigator will conduct the study according to applicable local or regional regulatory requirements and align his or her conduct in accordance with the “Responsibilities of the Investigator” that are listed in Appendix A Schedule of Study Procedures . The principles of Helsinki are addressed through the protocol and through appendices containing requirements for informed consent and investigator responsibilities

This trial was designed and will be performed according to the European Medicines Agency (EMA) recommendations CPMP/EWP/562/98: ‘Points to consider on clinical investigation of medicinal products in the chronic treatment of patients with chronic obstructive pulmonary disease (COPD)’ [29] and the EMA concept paper (CHMP/EWP/8197/2009) on the need for revisions of the aforementioned points to consider [30].

15.1 IRB and/or IEC Approval

IRBs and IECs must be constituted according to the applicable local requirements of each participating region. The sponsor or designee will require documentation noting all names and titles of members who make up the respective IRB or IEC. If any member of the IRB or IEC has direct participation in this study, written notification regarding his or her abstinence from voting must also be obtained.

The sponsor or designee will supply relevant documents for submission to the respective IRB or IEC for the protocol’s review and approval. This protocol, the Investigator’s Brochure, a copy of the informed consent form, and, if applicable, subject recruitment materials and/or advertisements and other documents required by all applicable laws and regulations, must be submitted to a central or local IRB or IEC for approval. The IRB’s or IEC’s written approval of the protocol and subject informed consent must be obtained and submitted to the sponsor or designee before commencement of the study (ie, before shipment of the sponsor-supplied drug or study specific screening activity). The IRB or IEC approval must refer to the study by exact protocol title, number, and version date; identify versions of other documents (eg, informed consent form) reviewed; and state the approval date. The sponsor will notify site once the sponsor has confirmed the adequacy of site regulatory documentation and, when applicable, the sponsor has received permission from competent authority to begin the trial. Until the site receives notification no protocol activities, including screening may occur.

Sites must adhere to all requirements stipulated by their respective IRB or IEC. This may include notification to the IRB or IEC regarding protocol amendments, updates to the informed consent form, recruitment materials intended for viewing by subjects, local safety reporting requirements, reports and updates regarding the ongoing review of the study at intervals specified by the respective IRB or IEC, and submission of the investigator’s final status report to IRB or IEC. All

IRB and IEC approvals and relevant documentation for these items must be provided to the sponsor or its designee.

Subject incentives should not exert undue influence for participation. Payments to subjects must be approved by the IRB or IEC and sponsor.

15.2 Subject Information, Informed Consent, and Subject Authorization

Written consent documents will embody the elements of informed consent as described in the Declaration of Helsinki and the ICH Guidelines for GCP and will be in accordance with all applicable laws and regulations. The informed consent form, subject authorization form (if applicable), and subject information sheet (if applicable) describe the planned and permitted uses, transfers, and disclosures of the subject's personal and personal health information for purposes of conducting the study. The informed consent form and the subject information sheet (if applicable) further explain the nature of the study, its objectives, and potential risks and benefits, as well as the date informed consent is given. The informed consent form will detail the requirements of the participant and the fact that he or she is free to withdraw at any time without giving a reason and without prejudice to his or her further medical care.

The investigator is responsible for the preparation, content, and IRB or IEC approval of the informed consent form and if applicable, the subject authorization form. The informed consent form, subject authorization form (if applicable), and subject information sheet (if applicable) must be approved by both the IRB or IEC and the sponsor prior to use.

The informed consent form, subject authorization form (if applicable), and subject information sheet (if applicable) must be written in a language fully comprehensible to the prospective subject. It is the responsibility of the investigator to explain the detailed elements of the informed consent form, subject authorization form (if applicable), and subject information sheet (if applicable) to the subject. Information should be given in both oral and written form whenever possible and in the manner deemed appropriate by the IRB or IEC. In the event the subject is not capable of rendering adequate written informed consent, then the subject's legally acceptable representative may provide such consent for the subject in accordance with applicable laws and regulations.

The subject, or the subject's legally acceptable representative, must be given ample opportunity to: (1) inquire about details of the study and (2) decide whether or not to participate in the study. If the subject, or the subject's legally acceptable representative, determines he or she will participate in the study, then the informed consent form and subject authorization form (if applicable) must be signed and dated by the subject, or the subject's legally acceptable representative, at the time of consent and prior to the subject entering into the study. The subject or the subject's legally acceptable representative should be instructed to sign using their legal names, not nicknames, using blue or black ballpoint ink. The investigator must also sign and date the informed consent form and subject authorization (if applicable) at the time of consent and prior to subject entering into the study; however, the sponsor may allow a designee of the investigator to sign to the extent permitted by applicable law.

Once signed, the original informed consent form, subject authorization form (if applicable), and subject information sheet (if applicable) will be stored in the investigator's site file. The investigator must document the date the subject signs the informed consent in the subject's medical record. Copies of the signed informed consent form, the signed subject authorization form (if applicable), and subject information sheet (if applicable) shall be given to the subject.

All revised informed consent forms must be reviewed and signed by relevant subjects or the relevant subject's legally acceptable representative in the same manner as the original informed consent. The date the revised consent was obtained should be recorded in the subject's medical record, and the subject should receive a copy of the revised informed consent form.

15.3 Subject Confidentiality

The sponsor and designees affirm and uphold the principle of the subject's right to protection against invasion of privacy. Throughout this study, a subject's source data will only be linked to the sponsor's clinical study database or documentation via a unique identification number. As permitted by all applicable laws and regulations, limited subject attributes, such as sex, age, or date of birth, and subject initials may be used to verify the subject and accuracy of the subject's unique identification number.

To comply with ICH Guidelines for GCP and to verify compliance with this protocol, the sponsor requires the investigator to permit its monitor or designee's monitor, representatives from any regulatory authority (eg, FDA, Medicines and Healthcare products Regulatory Agency, Pharmaceuticals and Medical Devices Agency), the sponsor's designated auditors, and the appropriate IRBs and IECs to review the subject's original medical records (source data or documents), including, but not limited to, laboratory test result reports, ECG reports, admission and discharge summaries for hospital admissions occurring during a subject's study participation, and autopsy reports. Access to a subject's original medical records requires the specific authorization of the subject as part of the informed consent process (see Section 15.2).

Copies of any subject source documents that are provided to the sponsor must have certain personally identifiable information removed (ie, subject name, address, and other identifier fields not collected on the subject's CRF).

15.4 Publication, Disclosure, and Clinical Trial Registration Policy

15.4.1 Publication and Disclosure

The investigator is obliged to provide the sponsor with complete test results and all data derived by the investigator from the study. During and after the study, only the sponsor may make study information available to other study investigators or to regulatory agencies, except as required by law or regulation. Except as otherwise allowable in the clinical study site agreement, any public disclosure (including publicly accessible websites) related to the protocol or study results, other than study recruitment materials and/or advertisements, is the sole responsibility of the sponsor.

The sponsor may publish any data and information from the study (including data and information generated by the investigator) without the consent of the investigator. Manuscript authorship for any peer-reviewed publication will appropriately reflect contributions to the production and review of the document. All publications and presentations must be prepared in accordance with this section and the Clinical Study Site Agreement. In the event of any discrepancy between the protocol and the Clinical Study Site Agreement, the Clinical Study Site Agreement will prevail.

15.4.2 Clinical Trial Registration

In order to ensure that information on clinical trials reaches the public in a timely manner and to comply with applicable laws, regulations and guidance, Takeda will, at a minimum register interventional clinical trials it sponsors anywhere in the world on ClinicalTrials.gov or other publicly accessible websites before start of study, as defined in Takeda Policy/Standard. Takeda contact information, along with investigator's city, country, and recruiting status will be registered and available for public viewing.

For some registries, Takeda will assist callers in locating trial sites closest to their homes by providing the investigator name, address, and phone number to the callers requesting trial information. Once subjects receive investigator contact information, they may call the site requesting enrollment into the trial. The investigative sites are encouraged to handle the trial inquiries according to their established subject screening process. If the caller asks additional questions beyond the topic of trial enrollment, they should be referred to the sponsor.

Any investigator who objects to Takeda providing this information to callers must provide Takeda with a written notice requesting that their information not be listed on the registry site.

15.4.3 Clinical Trial Results Disclosure

Takeda will post the results of clinical trials on ClinicalTrials.gov or other publicly accessible websites, as required by Takeda Policy/Standard, applicable laws and/or regulations.

15.5 Insurance and Compensation for Injury

Each subject in the study must be insured in accordance with the regulations applicable to the site where the subject is participating. If a local underwriter is required, then the sponsor or sponsor's designee will obtain clinical study insurance against the risk of injury to clinical study subjects. Refer to the Clinical Study Site Agreement regarding the sponsor's policy on subject compensation and treatment for injury. If the investigator has questions regarding this policy, he or she should contact the sponsor or sponsor's designee.

Appendix A Schedule of Study Procedures

Activities and assessments	Run-in period			Double-blind treatment period				FU safety visit ^{a)}
			R				VE	
Visit	V0	V1	V2	V3	V4	V5	V6	V7
Weeks	-6	-2	0	≤2	6	14	16	≤18
Visit Window (days) ^{b)}		-2 / +3	-3 / +5		-3 / +5	-3 / +5	-7 / +7	
Subject Information and Informed Consent	X							
Demographic data	X							
Medical History and concomitant diseases	X							
COPD history	X							
Inclusion/Exclusion criteria	X							
Withdrawal of disallowed medications	X							
Previous and concomitant medications	X	X	X	X	X	X	X	X
Substance use (smoking status)	X	X	X		X	X	X	
Physical examination	X		X				X	X
Vital signs and body measurements (including body weight and body height) ^{c)}	X	X	X	X	X	X	X	X
Subject fasting, avoidance of strenuous exercise and smoking	X	X ^{d)}	X	X*	X*	X*	X	X*
Standard laboratory (including blood pregnancy test) ^{e)}	X	X ^{d)}					X	
Urine analysis	X							
Urine pregnancy test ^{e)}		X	X		X	X		
Clotting time and platelet count	X	X				X		
Blood sampling for assessment of inflammatory biomarkers and metabolites in blood serum		X			X	X		
Sputum induction and sputum sample processing		X			X	X		
Bronchoscopy/bronchial biopsy			X				X	
Pulse oximetry measurement			X				X	
Chest X-ray or CT scan ^{f)} GERMANY ONLY: Check of historical chest X-ray or CT scan ^{f)}	X							
ECG (12-lead) at rest ^{g)}	X							
Pulmonary function test	X		X				X	

Activities and assessments	Run-in period			Double-blind treatment period				FU safety visit ^{a)}
Randomization criteria check			X					
Randomization			X					
ID card dispensed	X							
Adverse event assessment (see Section 10.0)	X	X	X	X	X	X	X	X
Dispense trial treatment	X		X		X			
Trial treatment returned			X		X		X	
Tablet compliance check			X ^{b)}		X		X	
Termination of double-blind treatment phase of the trial							X	

Notes:

- V3 and V7, which are safety visits only, are to be conducted within two weeks after bronchoscopy. The exact timing remains at the discretion of the Investigator.
- Assessments described under V6 (VE) are mandatory for randomized Subjects upon trial completion either prematurely or as scheduled.
- In selected Subjects three protected brush specimen in a middle lobe bronchus will be collected at visits V2 and V6. This is described in a separate sub-trial protocol. With regard to Subject consent and information this sub-trial is independent from the RO-2455-402-RD trial protocol (see Section 9.1.15.3).
- *For visits where subjects will not undergo blood draws or biopsies, the fasting requirement will only be mandated if clinically indicated as per investigator judgement.

Abbreviations:

R - Randomization (V2); V0 - visit 0, VE - visit end (V6), FU safety visit - follow-up safety visit (V7)

^{a)} Applies only to Subjects, who underwent the second bronchoscopy/bronchial biopsy at V6.

^{b)} Time windows for the run-in period always refer to V0, whereas those for the treatment period always refer to the randomization visit V2.

^{c)} Body height measurement only at visit V0.

^{d)} If confirmation or check of V0 laboratory values is necessary. Pregnancy test is optional.

^{e)} For female Subjects of childbearing potential or less than 1 year postmenopausal.

^{f)} If not performed within past three months. Examination results must be available.

GERMANY ONLY: Every patient should have a historical X-ray or CT scan available to clarify the exclusion criteria #18.

^{g)} This should be done prior to pulmonary function test.

^{h)} Tablet compliance calculation by the investigational site (see Section 9.2) to check for randomization criterion no. 2 (see Section 7.3).

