7.5 Diet, Fluid, Activity Control

Subjects should not take any food or drink overnight for at least 8 hours prior to returning to the study center for all visits. Subjects will also be asked to avoid strenuous exercise for 8 hours prior to each study visit and to avoid smoking for 4 hours prior to each study visit. For visits where subjects will not undergo blood draws or biopsies, the fasting requirement will only be mandated if clinically indicated as per investigator judgment.

Study medication will be administered once daily in the morning after breakfast with water. On study visit days where the subject is required to fast, study medication will be taken with water only.

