9.1.9 Procedures for Clinical Laboratory Samples

The central laboratory will provide the sites with appropriate material and a manual before the trial starts.

All samples will be collected in accordance with acceptable laboratory procedures. The maximum volume of blood at any single visit is approximately 18,5 mL, and the approximate total volume of blood for the study is 58 mL for all scheduled visits. Details of these procedures and required safety monitoring will be given in the laboratory manual.

Table 9.a Clinical Laboratory Tests

Hematology	Serum Chemistry	Urinalysis
Haemoglobin	Glucose	Glucose
Haematocrit,	Creatinine	Protein
Erythrocytes	Total bilirubin (in case of values above the normal range, direct and indirect bilirubin will be determined),	Blood
Thrombocytes,	Alkaline phosphatase (AP)	
Leukocytes	Aspartate aminotransferase (AST)	
Differential white blood cell (WBC) count	Alanine aminotransferase (ALT)	
	Gamma-Glutamyl transferase (GGT)	
	Creatine kinase (CK)	
	Sodium	
	Potassium	
	Total calcium	
	Cholesterol (total, low density lipoprotein, high density lipoprotein)	
	Triglyceride	
Other:		
Serum	Urine	
Female subjects of childbearing potential: human chorionic gonadotropin (hCG) for pregnancy	Female subjects of childbearing potential: hCG for pregnancy	

The central laboratory will perform laboratory tests for hematology, serum chemistries, and urinalysis.

The results of laboratory tests will be returned to the investigator, who is responsible for reviewing and filing these results.

The investigator will maintain a copy of the laboratory accreditation and the reference ranges for the laboratory used.

Analyses will be done by a central laboratory. Blood samples will be handled and stored according to the instructions provided by the central laboratory. All laboratory samples have to be clearly and fully labelled according to the Central Laboratory Manual. The laboratory reports received by fax from the central laboratory will be reviewed, signed and dated by the Investigator and attached to the CRF (including corrected reports).

Blood must be drawn under fasting conditions (8 hours).

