9.1.9.2 Clotting Time and Platelet Count

Blood sampling will be performed at visits V0, V1, and V5. Analyses of the clotting screen (PT, APTT, TT, INR and platelet count) will be done by the Central Safety Laboratory. Blood samples will be handled and stored according to the instructions provided by the Central Safety Laboratory. All laboratory samples have to be clearly and fully labelled according to the Central Laboratory Manual. The laboratory reports received by fax from the Central Safety Laboratory will be reviewed, signed and dated by the Investigator and attached to the CRF (including corrected reports).

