9.1.17 Sputum Induction

Sputum will be induced and collected at visits V1 (-2 weeks), V4 and V5 (subsequent to six and 14 weeks of double-blind treatment respectively). Sputum samples will be collected and initially processed at the investigational sites. Further details on sputum induction procedures and sputum sample processing are provided in the Sputum Laboratory Manual 'Manual Sputum Induction and Processing in COPD studies (Differential Cell Counts and Biomarkers)' (see [Appendix H](#)).

To ensure adequate quality and consistency of sputum samples between investigational sites, centralized hands-on training sessions in sputum collection, handling and processing will be provided by the Sputum Laboratory.

The quality of sputum samples will be assessed on an ongoing basis. In case of major concerns by the central reader(s) at the Sputum Laboratory about the quality of the sputum samples further procedural steps will be discussed with the Sponsor.

Further operative details are defined in the Sputum Laboratory Manual (see [Appendix H](#)) and in the Central Laboratory Manual.

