9.1.18 Inflammatory Biomarkers in Blood Serum

9.1.18.1 Blood Withdrawal and Sample Handling Methods

Blood serum collection for measurement of inflammatory biomarkers will be performed at visits V1 (-2 weeks), V4 and V5 (subsequent to six and 14 weeks of double-blind treatment respectively).

Blood withdrawal for the measurement of inflammatory biomarkers will be performed at approximately the same daytime (± 2 hours) but at 10:00 am at the latest at each respective visit.

Further details are described in the Central Laboratory Manual.

9.1.18.2 Measurement of Variables Describing Concentration of Inflammatory Biomarkers and metabolites in Blood Serum

The following inflammatory biomarkers will be measured in the collected blood serum:

1. Inflammatory mediators
(Human InflammationMAP[®] v.1, RBM)

Biomarker analyses will be performed by the Biomarker Laboratory. Exact procedures how to handle blood drawing, blood processing, storing and shipment are described in Section 9.4 and in the Central Laboratory Manual.

Database print-outs of the analysis data will be provided to the Investigator in a timely manner subsequent to data unblinding and no later than trial closeout and have to be filed in the Investigator's file together with the CRF data of the respective Subject.

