9.3.2 Run-in / Visit V1 (4 weeks after baseline visit V0)

The following assessments or procedures will be performed:

- Concomitant medications (see Sections 7.6, 7.7, 9.1.7)
- Substance use (smoking status)
- Vital signs (e.g. heart rate, blood pressure) and body measurements (body weight) (see Section 9.1.4, 9.1.5)
- Standard laboratory if deemed necessary (see Section 9.1.9). Pregnancy test optional.
- Urine pregnancy test (see Section 9.1.10)
- Clotting time and platelet count (see Section 9.1.9.2)
- Blood sampling for assessment of inflammatory biomarkers and metabolomics in blood serum (see Section 9.1.18)
- Sputum induction and sputum sample processing (see Section 9.1.17)
- Adverse event assessment

Further procedures

The Subject will be asked to return to the investigational site for visit V2 two weeks after visit V1.

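### Appendix A makes fasting, exercise and smoking restrictions at V1, the serum and sputum baseline visit, depend on a laboratory recheck, contradicting Sections 7.5 and 9.3

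*Protocol*

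**What the plan says.** Appendix A has one row covering all three restrictions, "Subject fasting, avoidance of strenuous exercise and smoking". Its V1 cell is marked with footnote d, which reads "If confirmation or check of V0 laboratory values is necessary. Pregnancy test is optional". No other cell in that row carries this footnote.

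The body of the protocol sets the rule differently:

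- Section 7.5 on fasting: "Subjects should not take any food or drink overnight for at least 8 hours prior to returning to the study center for all visits". The same section asks for 8 hours without strenuous exercise and 4 hours without smoking before each visit. Its one relaxation concerns fasting alone, at visits with neither a blood draw nor a biopsy.
- Section 9.3 repeats the 4-hour and 8-hour rules for each trial visit, with the same single relaxation.
- Section 9.1.9 requires an 8-hour fast before clinical laboratory blood is drawn.

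Three samples are scheduled at V1 without any condition:

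- Clotting screen (9.1.9.2): "Blood sampling will be performed at visits V0, V1, and V5".
- Biomarker serum (9.1.18.1): "Blood serum collection for measurement of inflammatory biomarkers will be performed at visits V1 (-2 weeks), V4 and V5".
- Sputum (9.1.17): "Sputum will be induced and collected at visits V1 (-2 weeks), V4 and V5".

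The item that is conditional at V1 is the routine laboratory retest, in Section 9.3.2: "Standard laboratory if deemed necessary (see Section 9.1.9). Pregnancy test optional".

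**The concern.** The visit schedule states a different rule from the text at the one visit that supplies the baseline for the serum and sputum endpoints. Section 13.1.3.3 analyses those endpoints by ANCOVA on change from baseline, with the baseline value as covariate, and for these variables the baseline is V1.

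The route to a wrong sample is short. Tablets are normally taken after breakfast (7.5, 8.1.3), and biomarker blood must be drawn by 10:00 am (9.1.18.1). A subject not told to fast for V1 would therefore probably eat shortly before the baseline draw. Current smokers are eligible (7.1), and Section 6.2 itself notes that systemic inflammation markers are associated with smoking. The V1 serum also feeds the metabolite panel, which includes products of fat and carbohydrate metabolism (9.1.18.3).

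If V4 and V5 are then sampled under the full restrictions, baseline and follow-up differ in sampling conditions as well as in treatment. At stake are the precision of the baseline adjustment and the meaning of the within-arm changes.

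**Working it through.** No formula or stated figure is involved. The check sets the Appendix A row against what is sampled at each visit.

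| Visit | Restriction cell | Blood draw for all subjects | Sputum | Biopsy |
|---|---|---|---|---|
| V0 | X | standard laboratory, clotting | no | no |
| V1 | X, footnote d | clotting, biomarker serum | yes | no |
| V2 | X | none | no | yes |
| V3 | X* | none | no | no |
| V4 | X* | biomarker serum | yes | no |
| V5 | X* | clotting, biomarker serum | yes | no |
| V6 | X | standard laboratory | no | yes |
| V7 | X* | none | no | no |

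1. **Does the exemption in 7.5 and 9.3 reach V1?** No. It needs a visit without blood or biopsy, and V1 has two blood draws for all subjects. It also never covers exercise or smoking. Under the text, all three restrictions are mandatory at V1.

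2. **What does the table say at V1?** It makes all three conditional on a recheck of V0 laboratory values. That contradicts 7.5 and 9.3 on all three. It also contradicts 9.1.9 on fasting for the clotting draw, which falls under 9.1.9.2.

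3. **Where does footnote d belong?** Its two parts match the two conditions that 9.3.2 puts on the standard laboratory item at V1: retest if needed, pregnancy test optional. The Appendix A standard laboratory row carries footnote d at V1 correctly. A remark about a pregnancy test has no meaning in a fasting row.

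4. **Is it a reading error from the PDF?** Unlikely. The revised schedule reproduced in Appendix L shows the same superscript in the same cell.

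5. **What about V4 and V5?** The asterisk note confines itself to visits without blood draws or biopsies. Blood is drawn at both, so it waives nothing there. Of the three serum and sputum sampling visits (V1, V4, V5), the table makes the restrictions conditional at one, and that one is the baseline.

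6. **How many variables use V1 as baseline?** The 46-marker panel is measured in serum and in sputum, and four sputum cell types are reported as absolute counts and as percentages: 46 + 46 + 4 + 4 = 100 listed variables. This shows reach, not effect.

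7. **Which analyses are untouched?** CD8+ and CD68+ use V2 and V6, both plain X. Neither of the two confirmatory tests is affected.

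8. **Direction of the effect on the rest.** V1 precedes randomization, so sampling conditions at V1 cannot depend on the assigned arm. The baseline covariate may become noisier, which weakens the adjustment. The unadjusted change from V1 within each arm may include a shift due to fasting or smoking state.

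**The case against.** The strongest reply is that this is a misplaced superscript that a careful reader would see through. Sections 7.5 and 9.3 state the rule in full, Section 1.3 lists it among the main changes of Amendment 12, and the pregnancy-test wording makes the footnote visibly out of place. Harm requires a site to follow one table cell over two explicit sections, and the protocol nowhere says that sites work from the table alone. This limits the likelihood of harm. It does not remove the contradiction: Section 9.3 has subjects return according to Appendix A, and the protocol gives no rule on which text prevails.

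Three narrower objections also have force:

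- A site loose enough to skip fasting at V1 might misread the asterisk at V4 and V5 too, which would shrink the fasting contrast. That is possible. The asterisk note covers fasting only, however, so the smoking and exercise contrast would remain.
- Section 9.1.9 concerns clinical laboratory blood. Biomarker serum has its own section, 9.1.18, which fixes time of day and is silent on fasting. This is correct, so 9.1.9 supports the point only for the clotting draw. The conflict with 7.5 and 9.3 does not depend on it.
- The count of 100 includes the same four cell types twice, and Section 9.1.17.2 treats 40 of the 46 panel markers as explorative. It should not be read as a measure of importance.

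**Conclusion.** The concern holds, as a minor point. Current Appendix A states a wrong rule for one cell, and that cell governs the only pre-randomization biomarker serum and sputum samples. (V0 includes routine serum chemistry but no biomarker serum.)

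The consequence rests on the assumption that at least some sites follow the schedule table at V1. If they do, the secondary and exploratory serum and sputum analyses may have a noisier baseline, and their descriptive within-arm changes become harder to interpret. The protocol offers no figure for the effect of an unfasted or post-smoking sample, so the size of the loss cannot be stated. The between-arm comparison is not biased, and the primary and key secondary biopsy endpoints are unaffected.

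**What to change.** In the Appendix A row for fasting, exercise and smoking, replace the V1 entry with a plain X and keep footnote d for the standard laboratory row only.

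Optionally, for clarity, also replace the asterisked entries at V4 and V5 with a plain X, since blood is drawn at both visits, and keep the asterisk at V3 and V7, where it does apply.

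The cost is one superscript removed and, if the optional change is made, two asterisks replaced. No visit, procedure or data field is added, and subjects are asked for nothing beyond what Sections 7.5 and 9.3 already require.
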